6.4 Protocol deviations

Researchers participating in the experiment will follow the experimental requirements for the corresponding operations and data recording. Any events that deviate from the original trial protocol must be recorded with the time of occurrence and specific reasons, and any deviations from the trial protocol must be explained.

7.Evaluation

7.1 Efficacy evaluation

The efficacy evaluation methods for different interventions include, but are not limited to: postoperative assessment of symptoms and signs, postoperative ultrasound assessment of the urinary system, postoperative evaluation of urination-related parameters, postoperative urinalysis and urine culture assessment, and postoperative surveys on urination function-related questionnaires.

7.2 Safety evaluation

7.2.1 Baseline vital signs and symptoms

When conducting a safety assessment, it is first necessary to understand the baseline vital signs and symptoms of the test subjects. This includes measuring their body temperature, pulse, respiratory rate, and blood pressure, while noting any specific symptoms such as dizziness, nausea, vomiting, etc. Preoperative hematological examinations and imaging studies should be completed, along with preoperative urinalysis, urine culture, and preoperative voiding function questionnaire assessments. Additionally, the patient's medical history must be clarified and cross-checked against the trial's inclusion and exclusion criteria one by one to ensure

that the patient population has no surgical contraindications and fully meets the enrollment criteria. These baseline data will serve as reference indicators for the assessment.

7.2.2 Laboratory examinations

The continuity indicators describe the measured values of each research subject after surgery and the change values relative to the preoperative baseline. The laboratory indicators are divided into low, normal, and high according to the normal value range. Describe the situations where the values change from normal or high at baseline to low after baseline, and where the values change from normal or low at baseline to high after baseline. The low or high values after baseline are calculated using the minimum or maximum observed value after baseline. Doctors will evaluate these abnormal indicators to determine whether their abnormalities have clinical significance. Describe the proportion of "abnormal and clinically significant" among the subjects with abnormal changes.

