7.2.2 Laboratory examinations

The continuity indicators describe the measured values of each research subject after surgery and the change values relative to the preoperative baseline. The laboratory indicators are divided into low, normal, and high according to the normal value range. Describe the situations where the values change from normal or high at baseline to low after baseline, and where the values change from normal or low at baseline to high after baseline. The low or high values after baseline are calculated using the minimum or maximum observed value after baseline. Doctors will evaluate these abnormal indicators to determine whether their abnormalities have clinical significance. Describe the proportion of "abnormal and clinically significant" among the subjects with abnormal changes.

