11.1 Sample size determination

The sample size is calculated based on a differential test, with urinary dysfunction as the primary endpoint. Based on our preliminary research results, we estimate the

incidence of urinary dysfunction in the bladder training group is 44.7%, and in the direct removal group, it is 59.3%. Patients are randomly assigned to the two groups in a 1:1 ratio. With a two-sided significance level α of 0.05 and a power $(1-\beta)$ of 80%, the sample size was calculated using PASS 15 software. Each group, the ICCAUT group and the free-drainage group, requires 180 cases. Assuming a dropout rate of 10%, each group requires 200 cases. Therefore, this trial needs a total of 400 cases.

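### Clinically significant laboratory abnormalities are given only as a share of patients whose values became abnormal, so a by-arm percentage could hide or reverse a difference in risk per patient

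*Protocol*

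**What the plan says.** Protocol v2.0, section 7.2.2, sets out the laboratory safety summary in four steps.

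- Classification: "The laboratory indicators are divided into low, normal, and high according to the normal value range".
- Shifts from the preoperative baseline: "Describe the situations where the values change from normal or high at baseline to low after baseline", and likewise for shifts to high. The worst later value counts: "The low or high values after baseline are calculated using the minimum or maximum observed value after baseline".
- Clinical judgement: "Doctors will evaluate these abnormal indicators to determine whether their abnormalities have clinical significance". No numerical threshold is given.
- Summary: "Describe the proportion of 'abnormal and clinically significant' among the subjects with abnormal changes".

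The wording is the same in the protocol text that preceded v2.0, and the table of changes lists no amendment to 7.2.2. The SAP does not restate or replace the rule. Its secondary endpoint table and its list of other outcomes (section 6.5.3) contain no general laboratory summary.

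**The concern.** The denominator in the last step is neither the randomised patients nor the tested patients. It is the patients who had an abnormal shift, and that group is complete only after the assigned catheter management has been given. If the assignment changes how many patients shift, the two arms' percentages describe differently selected groups, and randomisation no longer protects the comparison. Blinding the physicians does not cure this, because the denominators can differ even if every judgement of clinical significance is unbiased.

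At stake is the reading of one safety summary. An arm in which more patients have clinically significant abnormalities could show the same percentage as the other arm, or a lower one.

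**Working it through.** **Inputs.** Section 7.2.2 states no figure to reproduce. The only design number used is the arm size of 200, from protocol section 11.1: "Assuming a dropout rate of 10%, each group requires 200 cases". That figure checks. The unpooled two-proportion formula with 44.7% and 59.3%, two-sided 0.05 and 80% power gives 179.9, so 180 per group, and 180 / (1 − 0.10) = 200. The pooled formula gives 183. The point does not depend on this. All laboratory counts below are assumptions, because the documents give none.

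**Formulas.** In an arm of size N, let a be the number of patients with an abnormal shift and c the number of those judged clinically significant.

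- Percentage under 7.2.2: c / a.
- Risk per patient: c / N = (a / N) × (c / a).

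With equal N, arm B has the higher risk per patient if cB > cA. It shows the lower percentage under 7.2.2 if cB/aB < cA/aA, that is, if cB/cA < aB/aA. So:

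- reversal: 1 < cB/cA < aB/aA;
- complete masking: 1 < cB/cA = aB/aA;
- direction kept: cB/cA > aB/aA.

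**Results with assumed counts, N = 200 per arm.**

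| Arm A, c/a | Arm B, c/a | cB/cA | aB/aA | Shown under 7.2.2, A vs B | Per patient, A vs B | Outcome |
|---|---|---|---|---|---|---|
| 10/20 | 20/60 | 2.0 | 3.0 | 50.0% vs 33.3% | 5.0% vs 10.0% | reversed |
| 20/40 | 30/80 | 1.5 | 2.0 | 50.0% vs 37.5% | 10.0% vs 15.0% | reversed |
| 20/40 | 40/80 | 2.0 | 2.0 | 50.0% vs 50.0% | 10.0% vs 20.0% | masked |
| 20/40 | 50/80 | 2.5 | 2.0 | 50.0% vs 62.5% | 10.0% vs 25.0% | direction kept |
| 12/60 | 24/60 | 2.0 | 1.0 | 20.0% vs 40.0% | 6.0% vs 12.0% | direction kept |

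In the fourth row the direction is right but the contrast shrinks: a ratio of 62.5/50.0 = 1.25 is shown, where the ratio per patient is 25.0/10.0 = 2.5. In the fifth row equal numbers shift in both arms, and the rule does no damage. The rows show what is possible; they say nothing about how likely each case is.

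**The case against.** The case against has four parts.

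1. **No comparison is prescribed.** Section 7.2.2 asks for a description and names no arms, test or effect measure. Read literally, it asks what share of the abnormal changes the doctors thought mattered, which is a legitimate summary of the clinical review. This stands in part. The text does not say by arm, but in the safety section of a two-arm trial that is the natural presentation, and the point is conditional on it.

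2. **The same paragraph also describes the shifts.** If their counts are shown with arm sizes, a reader can multiply shift rate by conditional proportion and recover the risk per patient. This is true, but 7.2.2 requires neither counts by arm nor the number tested.

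3. **The main harm is covered elsewhere.** The only laboratory tests in the v2.0 schedule (Table 1) are urinalysis and urine culture. Urinary tract infection is a secondary endpoint, and SAP section 6.5.3 reports it, and complications within 30 days, as absolute risk differences with 95% CI. Under protocol section 8.3, abnormal results that come with symptoms, need intervention or are considered adverse events by the investigator are reported as adverse events. This stands and keeps the point small.

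4. **The counts are invented.** This also stands. Nothing in the documents indicates that abnormal shifts would rise proportionally more than clinically significant ones.

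A reader might infer that training will look safer than it is, or that the trial's safety conclusion would point the wrong way. The documents do not support either reading. Reversal needs the specific condition shown above, no laboratory rates are given, and the separate reporting of infection, complications and adverse events does not use this denominator.

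**Conclusion.** The point holds as a minor correction to a descriptive rule. Section 7.2.2 specifies a denominator that is settled after randomisation and offers no other for clinically significant abnormalities. Shown by arm, the percentage would not be a randomised comparison. It would mask a difference in risk per patient when shifts rise in the same proportion as clinically significant abnormalities, and reverse it when they rise more.

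The size in this trial cannot be estimated, because no laboratory rates are given. The conclusion rests on the summary being tabulated by arm and on the assigned management being able to change the number of abnormal shifts. No endpoint and no output listed in the SAP is affected.

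**What to change.** In protocol section 7.2.2, and in a short SAP table, report by arm n/N and the percentage for two categories: abnormal change, and abnormal change judged clinically significant. Let N be all randomised patients in that arm with a baseline and at least one post-baseline value for that test. Keep the proportion among patients with abnormal changes only as a supplement.

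A risk difference with 95% CI, in line with the SAP's convention for categorical variables (section 6.1), is optional and should be labelled descriptive.

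The cost is one extra descriptive table. For the urine tests no new measurements are needed, since protocol section 12.1 lists both preoperative and pre-removal results in the CRF. Sample size, conduct and the endpoint analyses are unchanged.

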7.2.3 Physical examination and vital signs

Physical Examination: General examination, head examination, neck examination, thorax and lung examination, heart and vascular examination, abdominal examination, spine and limbs examination, and neurological examination. Vital signs include routine blood pressure, heart rate, body temperature, etc. Statistical descriptions are provided for the measurement values of physical examination, vital signs, and weight before and after treatment relative to the baseline. Abnormal vital signs or those exceeding the normal value range are described.

8. Adverse event reporting

8.1 Adverse events

Adverse events in the study include complications and death events within 30

days after surgery. All adverse events reported spontaneously by the subjects or observed by the staff will be recorded in the database and promptly reported to the trial steering committee.

8.2 Definition of adverse events

An adverse event is defined as any untoward experience occurring in a subject during the study, regardless of whether it is considered to be related to catheter clamping. All adverse events reported spontaneously by the trial subject or observed by the investigator or their staff will be recorded.

8.3 Abnormal test results.

Abnormal test results should be evaluated to determine whether they should be reported as adverse events based on the following criteria for objective test values: 1) Test results are accompanied by symptoms; 2) Test results require medical or surgical intervention; 3) The investigator considers the test result to be an adverse event.

If none of the above criteria are met, merely repeating an abnormal test does not constitute an adverse event. Test results judged by the investigator to be erroneous do not need to be reported as adverse events.

8.4 Serious adverse events

Serious adverse events include any of the following adverse medical events: 1) Events or effects leading to death; 2) Life-threatening events; 3) Events requiring hospitalization or prolonging the hospital stay of an inpatient; 4) Events resulting in persistent or significant disability or incapacity. Upon learning of a serious adverse event that is life-threatening or leads to death, it must be reported within 7 days. Other serious adverse events must be reported within 15 days. All adverse events are followed up immediately after they occur, until the event stabilizes or improves. Depending on the specific situation, follow-up may require additional tests or medical

procedures, or further referral.

8.5 Severity assessment

The severity of adverse events will be assessed using the Clavien-Dindo classification of complications.

8.6 Causality assessment

The causality of adverse events with respect to the intervention will be subjectively assessed by the investigator.

9. Data processing and storage

Clinical research data will be recorded through the perioperative eCRF, including perioperative information, pathological data, and follow-up information. To protect patient privacy, patient identification numbers will not be disclosed to data analysts.

All patients will be coded and identified using random numbers. These random numbers do not include patient initials or date of birth. Members of the trial steering committee will have a decoding list that specifies the random numbers of patients in the database and their identification numbers.

All patients who meet the inclusion criteria will be registered, including those who refuse randomization, those excluded due to exclusion criteria, and those who are withdrawn after randomization due to withdrawal criteria. Reasons for exclusion and withdrawal will be recorded.

10. Quality management

The key to the quality control of the trial lies in:

(1) Blinding quality control

The implementation of blinding in this study may affect the quality of the

research, particularly the achievement of the primary endpoint. If the trial is not blinded to surgeons, it may influence their judgment on whether the patient needs secondary catheterization based on whether bladder training was performed. If the ultrasound imaging physicians are not blinded, it may affect their assessment of residual urine volume in the bladder based on their knowledge of the patient's intervention. Therefore, blinding the randomization information from surgeons and ultrasound imaging physicians is one of the key aspects of quality control in this experiment. To this end, the study requires patients and nurses to keep the patient's group assignment confidential from surgeons and ultrasound imaging physicians. Surgeons and ultrasound physicians must also consciously adhere to the principle of not inquiring about the patient's group assignment. Any premature unblinding must be recorded, including the reason and time of unblinding.

(2) Interventional method quality control

The implementation quality of the interventional method is the second key point of quality control in this study. To address this, the study implements quality control in the following aspects: 1) All assigned nurses receive training, which includes standardized procedures for clamping and unclamping the urinary catheter, as well as the standardized operation for obtaining urine routine and urine culture before catheter removal; 2) After the patient signs the informed consent and is enrolled, the assigned physician is clearly informed not to provide clinical advice on whether to clamp the catheter and not to participate in any operations related to bladder training.

Additionally, the trial management group communicates with the patient that if the assigned physician suggests bladder training, the patient should promptly report to the assigned nurse and the trial steering committee. The trial steering committee will then communicate again with the assigned physician and emphasize the quality control points of the trial; 3) The start of training is uniformly set for 9:00 am on the first postoperative day, and the removal of the catheter is uniformly set for 9:00 am the next day. It is not recommended to advance or delay the catheter removal time. Any orders to advance or delay the catheter removal must be communicated to the trial steering committee members before execution, with reasons provided. If the trial

steering committee deems the reason valid, the order to advance or delay the catheter removal is allowed to be executed; 4) Nurses need to educate and guide enrolled patients to ensure that patients in the bladder training group actively perform forceful urination during each period of unclamping to assist in urine discharge; 5) Patients in the bladder training group, if unable to persist in reaching the specified catheter clamping time (less than 3 hours of catheter clamping before feeling the urge to urinate), may end a training cycle early, open the catheter for 5 minutes, and then start the next clamping training cycle; 6) Before catheter removal, patients in the bladder training group must complete the Bladder Training Quality Self-Assessment Form; 7) During the first catheterization, selective α 1-adrenergic receptor blockers (such as tamsulosin) should not be used. If medically necessary, the patient must withdraw from the trial.

(3) Endpoint quality control

Our project team requires all levels of physicians in our department to strictly follow the bladder residual urine assessment method and the criteria for secondary catheterization as stipulated in the project research plan to calculate bladder residual urine and decide whether to perform secondary catheterization. To reduce bias in the measurement of bladder residual urine, this study implements quality control in the following two aspects: 1) A fixed radiologist is responsible for assessing bladder residual urine, and this physician has specialized in abdominal digestive and urinary system ultrasound examinations for over 10 years; 2) The ultrasound diagnosis location is set in the same therapeutic area as the patient, ensuring that patients can undergo immediate ultrasound examination after the first urination following catheter removal, avoiding the impact on the judgment of residual urine due to a long interval between urination and ultrasound examination.

To ensure the collection of primary and secondary endpoints, this study will appoint a supervisory nurse to serve as the Clinical Research Coordinator (CRC). The CRC will daily verify the patient's enrollment, withdrawal, achievement of primary endpoints, and measurement of secondary endpoints. They will remind physicians to perform relevant medical orders, nurses to execute medical orders and collect data,

and patients to fill out the required questionnaires and self-assessment forms in a timely manner. Additionally, the study will arrange for two graduate students to work with the CRC to promptly enter data into the Electronic Case Report Form (eCRF) and the database (Epidata).

(4) Regular education for healthcare personnel involved in the study.

The research group of this project will conduct regular education for all physicians and nurses involved in the study on a monthly basis. The main content of the education includes the three quality control aspects mentioned above: blinding quality control, interventional method quality control, and endpoint quality control. This ensures that physicians and nurses can strictly follow the quality control requirements of the study for related operations and ensures the quality of the intervention operations performed by nurses on enrolled patients.

11. Statistical analysis

11.1 Sample size determination

The sample size is calculated based on a differential test, with urinary dysfunction as the primary endpoint. Based on our preliminary research results, we estimate the incidence of urinary dysfunction in the bladder training group is 44.7%, and in the direct removal group, it is 59.3%. Patients are randomly assigned to the two groups in a 1:1 ratio. With a two-sided significance level α of 0.05 and a power $(1-\beta)$ of 80%, the sample size was calculated using PASS 15 software. Each group, the ICCAUT group and the free-drainage group, requires 180 cases. Assuming a dropout rate of 10%, each group requires 200 cases. Therefore, this trial needs a total of 400 cases.

11.2 Analysis population

11.2.1 Full analysis set

The comparative analysis of the primary outcomes will be conducted on the basis

of the "modified intention-to-treat (mITT)". The mITT analysis will include patients who did not follow the randomly assigned measures but were not excluded according to the withdrawal criteria. In this study, if a patient meets the withdrawal criteria after randomization, this patient will be excluded, and the relevant data of this patient will not appear in the statistical analysis including the mITT analysis. In the mITT analysis, for patients randomly assigned to the bladder training group, if the catheter is directly removed without undergoing training at the end, the analysis will still be carried out according to the bladder training group; for patients randomly assigned to the direct removal group, if they receive bladder training at the end, the analysis will still be carried out according to the direct removal group. In addition, if a patient undergoes secondary catheterization, does not meet the withdrawal criteria, but the urine volume drawn after secondary catheterization is less than 100ml. We will not consider that this secondary catheterization is caused by bladder emptying disorder. In the analysis, we will not classify such patients as having urinary dysfunction. In the mITT analysis, we will still include these patients in the analysis, but instead of classifying them as end-point events (positive events), we will analyze them as negative events.

Specific possible reasons for not following the randomization procedure include:

- 1) The patient's urine becomes cloudy during the postoperative catheterization period, and the physician suspects a urinary tract infection, thus not recommending bladder training;
- 2) The patient cannot tolerate catheter clamping and refuses bladder training;
- 3) The patient refuses to follow the assigned procedure;
- 4) The nurse fails to perform the operation according to the assigned method;
- 5) The catheter is not removed on the second postoperative day, either earlier or later (but not beyond the fifth postoperative day).

The study needs to record the specific reasons for not following the planned procedure.

